#### **4.8.4 Follow-up after adverse event**

After initially recording an AE or recording and reporting an SAE/SAR, the Investigator is required to follow each participant until resolution. Follow up information on an SAE/SAR should be reported to the ICNARC CTU using the MOSAICC SAE Report Form. AEs and SAEs should be followed up until resolution or death of the trial subject.

#### **4.8.5 Reporting to REC and MHRA**

Annual study progress reports and Developmental Safety Update Reports will be submitted to the REC and MHRA, respectively. These reports will be submitted yearly on the anniversary of REC favourable opinion and Clinical Trial Authorisation approval.

**Figure 1. Safety reporting**

\* AEs requiring recording/reporting are specified in 4.8.3 and Appendix 2 of the protocol. Those not requiring recording/reporting will need to be documented in the patient’s medical notes and followed up until resolution.

† If there is any uncertainty about whether the SAE is associated with trial treatment, then it should be reported.

## 4.9 Data collection

### 4.9.1 CMP data

To maximise efficiency, trial data collection will be nested within the Case Mix Programme 'Research Platform', enabling data collection to be incorporated within the routine Case Mix Programme data collection processes, streamlining data linkage. Data from the Case Mix Programme to be used in MOSAICC will include:

- baseline demographics and risk factors;
- secondary outcomes of critical care unit and acute hospital mortality, organ support (calendar days of organ support in critical care for the CCMDS), duration of critical care and acute hospital stay; and
- critical care costs, based on Health Care Resource Groups, from the index admission and any subsequent critical care readmissions.

### 4.9.2 Other routine data sources

All patients recruited to the trial will be asked to provide consent for data linkage with other routine data sources. Data from other routine sources will include:

- date of death for deaths occurring after discharge from acute hospital, by data linkage with civil registrations mortality data held by NHS Digital, until longest available follow-up (e.g. patients recruited in the first month of the trial will be able to be followed-up for survival until 24 months); and
- hospital costs for subsequent hospitalisations, by data linkage to Hospital Episode Statistics held by NHS Digital and Patient Episodes Data for Wales held by Digital Health and Care Wales.
- on-going requirement for KRT at 90 days and one year, by data linkage with the UK Renal Registry.

### 4.9.3 Additional data collection

Additional data items collected at each site specifically for the trial will be limited to:

- confirmation of eligibility criteria and patient/legal representative consent;
- patient and personal legal representative contact details for questionnaire follow-up at 90 days and one year;
- data to monitor adherence with the intervention;
- data related to commencement of KRT; and
- adverse event reporting.

## 4.10 Questionnaire follow-up

Each participant will be followed up with a questionnaire up to a maximum of one year.

Survival status at 90 days and one year following randomisation will be obtained via data linkage with nationally held routine data. At each time point, survivors will be sent (via email or post as per their indicated preference at the time of consent) a questionnaire by the ICNARC CTU containing the EuroQol EQ-5D-5L and health services questionnaires. These questionnaires are designed to take no longer than 15 minutes to complete and if completing a postal questionnaire, patients will be provided with a pen and stamp-addressed envelope for ease of return.

Non-responders will be telephoned three weeks after the questionnaire was posted and asked to check whether they have received the questionnaire. If preferable for the patient, they will be offered the option of either being sent another copy of the questionnaire, completing the

questionnaire over the telephone with a trained member of the MOSAICC Trial team, or to receive the questionnaire in a preferred alternative format (e.g. e-mail).

If a patient is an in-patient at a participating site at either of the follow-up time-points, the site research team will be asked to approach the patient and conduct the questionnaire with them in hospital, if willing and if their condition permits.

If a patient is on their initial acute hospital admission at either of the follow-up time points, they will not be asked to complete the health services questionnaire, as this contains only questions that are relevant following discharge from acute hospital.

#### **4.11 Data management**

All participant data collected will be entered onto a secure electronic data entry system. The option of entry first onto paper CRFs will be available. The site PIs will oversee and be responsible for data collection, quality and recording. Collection of data can be delegated (as per the Delegation Log) by the site PIs to qualified members of the research team.

Data entered onto the secure electronic data entry system will undergo validation checks for completeness, accuracy and consistency of data. Queries on incomplete, inaccurate or inconsistent data will be sent to the local research team at participating sites for resolution.

Security of the electronic data entry system is maintained through user names and individual permissions approved centrally by the ICNARC CTU. Central back-up procedures are in place. Storage and handling of confidential trial data and documents will be in accordance with the Data Protection Act. ICNARC is registered under the Data Protection Act (Registration number: Z6289325).

## **5 STATISTICS AND DATA ANALYSIS**

### **5.1 Sample size**

To achieve 90% power to detect a clinically meaningful absolute reduction in 90-day mortality of 7% ( $p < 0.05$ ) from 59% to 52% (a conservative estimate of half the treatment effect (OR 0.75) observed in the AKIN 2-3 subgroup from the BICAR-ICU Trial), and allowing for 6% withdrawal/refusal of deferred consent (based on figures from the 65 trial), we will recruit a total sample size of 2250 patients.

Based on 2018 CMP data, 6139 patients meeting the proposed inclusion criteria (during the first 24 hours of admission) were treated in participating critical care units. Assuming the proportions of eligible patients recruited on previous similar RCTs and a recruitment rate of approximately 1.3 patients per site per month will allow recruitment of the full sample within 34 months from 60 critical care units, allowing for a staggered opening of sites opening over a six-month period.

### **5.2 Statistical analysis**

#### **5.2.1 Internal pilot analysis**

Data will be analysed at the end of the internal pilot trial stage. The analysis will take place in month 14 of the trial to allow data to be collected and entered to assess all progression criteria. If all the green criteria are met, the trial will progress from the internal pilot to the full trial unchanged. If any of the amber criteria are met, the trial will be amended to address the issues raised. If any of the red criteria are met, the trial will stop.

The final decision on progression from the pilot stage to the full trial will be made by the NIHR HTA programme after recommendation by the TSC.

### 5.2.2 Clinical effectiveness analysis

All analyses will be described in a statistical analysis plan, a priori, before the investigators are unblinded to any study outcomes. All analyses will follow the intention to treat principle. The intention to treat population will include all patients randomised to the trial according to the group to which they were allocated, other than if a patient or their legal representative requests removal of all data from the trial (see 4.6.2). Baseline patient characteristics will be compared between the two groups to observe balance and the success of randomisation. These comparisons will not be subject to statistical testing. The delivery of the intervention will be described in detail. Results will be reported in accordance with the CONSORT statement. Missing data (including missing outcomes) will be multiply imputed using chained equations, including treatment allocation, covariates and outcomes in all imputation models.

Analysis of the primary outcome (90-day mortality) will be adjusted for site (as stratification variable) and additional baseline covariates. An analysis adjusted only for site will also be conducted to aid interpretation. Treatment effects will be estimated using generalised linear mixed models (GLMMs), including a random effect of site, with the binomial family and identity link to estimate absolute risk reduction and the Poisson family and log link to estimate relative risk. Adjustment for baseline covariates can increase the precision of the estimate of treatment effect, and therefore the power of the study, and adjust for any chance imbalance between the treatment groups. The covariates for inclusion in the adjusted analysis will be selected a priori based on established relationship with outcome for critically ill patients, and not because of observed imbalance, significance in univariable analyses or by stepwise selection method.

Analyses of secondary outcomes will use similar GLMMs with the binomial/Poisson family for binary outcomes (mortality at critical care unit discharge and 28-days; receipt of respiratory, renal and cardiovascular support; on-going requirement for KRT) and normal family for continuous outcomes (duration of organ support; health-related quality of life). Analyses of duration of critical care unit and acute hospital stay will be performed by Wilcoxon rank-sum tests, stratified by survival status. Survival will be presented as Kaplan-Meier plots and analysed by Cox proportional hazards models with shared frailty at the site level.

Subgroup analyses will test for an interaction between treatment group and subgroup (for a limited number of subgroups specified a priori) in the adjusted GLMM for the primary outcome on the relative risk scale. One of the key subgroups will include severity of the acidosis.

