### 4.2 Setting

60 adult NHS critical care units (defined as intensive care and combined intensive care/high dependency units) in the United Kingdom and participating in the national Case Mix Programme.

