## 4.4 Recruitment and consent

### 4.4.1 Randomisation

Participants will be randomised 1:1 to receive IV 8.4% w/v sodium bicarbonate infusion (intervention) or no IV sodium bicarbonate (comparator) with randomised permuted blocks of variable block sizes, stratified by site.

A central web-based randomisation/treatment allocation system will be used. The service will be available 24 hours a day, seven days a week. The research/clinical team will randomise and co-

ordinate the treatments. Sodium bicarbonate will be available on the critical care unit and, following prescription, will be administered by one of the clinical team caring for the patient.

Following randomisation into MOSAICC, each participant will be assigned a unique MOSAICC Trial Number and a CRF will be completed by the local team (see section 4.7.4)

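### The covariate-adjusted identity-link binomial mixed model for the absolute risk reduction is likely to fail or reach a boundary if the covariates are strongly prognostic

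*Protocol*

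**What the plan says.** Protocol 5.2.2 (Clinical effectiveness analysis) states that analysis of the primary outcome will be "adjusted for site (as stratification variable) and additional baseline covariates". Treatment effects come from generalised linear mixed models with a random site effect: one "with the binomial family and identity link to estimate absolute risk reduction", and a second with Poisson family and log link for the relative risk. Covariates are to be fixed in advance on the strength of their known relationship with outcome. The section gives gains in precision and power as a reason for adjusting. It also plans a site-only analysis, and multiple imputation of missing data.

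The sample size in Protocol 5.1 is set on the absolute scale: "To achieve 90% power to detect a clinically meaningful absolute reduction in 90-day mortality of 7" percentage points, from 59% to 52%. It continues "allowing for 6% withdrawal/refusal of deferred consent", and "we will recruit a total sample size of 2250 patients". Protocol 4.2 plans "60 adult NHS critical care units".

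**The concern.** With an identity link, the model adds covariate effects directly to the risk. Nothing stops the sum passing 0 or 1 for a patient with extreme covariate values, and outside that range the binomial likelihood is undefined. The fitting routine then either fails or ends on a boundary, where the usual theory for standard errors does not apply. The protocol asks for strong predictors, for the sake of precision, in a model that is comfortable only with weak ones.

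At stake is the adjusted risk difference, which is the scale on which the trial is powered. If the model cannot be fitted as written, some other route to that estimate is needed, and it is better named now than found at analysis.

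**Working it through.** **Inputs from the protocol.** Risks 59% and 52%, 90% power, p<0.05, 6% loss and N = 2250 (5.1); 1:1 allocation (4.4.1); 60 units (4.2); model and covariate policy (5.2.2).

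**Assumed inputs.** The protocol does not give covariate number, type or strength. The range examined is one to five covariates, continuous or binary, with c-statistic 0.60 to 0.80. Covariates act on the log-odds scale. The between-site SD is 0.2 on the logit scale, which is about 0.2 × 0.59 × 0.41 = 0.05 on the risk scale.

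**Step 1: reproduce the sample size.** With mean risk 0.555 and two-sided alpha 0.05:

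n per arm = [1.960 × √(2 × 0.555 × 0.445) + 1.282 × √(0.59 × 0.41 + 0.52 × 0.48)]² / 0.07² = (1.377 + 0.898)² / 0.0049 ≈ 1057.1, so 1058.

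The total is 2116, and 2116 / 0.94 ≈ 2251 against the stated 2250. The figure reproduces. The number analysed is 2250 × 0.94 = 2115.

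**Step 2: a hand check of the mechanism.** The control mean leaves 1 − 0.59 = 0.41 of room before the risk reaches 1. For one normal covariate with log-odds SD s, the slope on the risk scale is roughly s × 0.59 × 0.41 per SD, so the limit is reached at 0.41 / slope SDs. With about 1057 controls:

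| c-statistic | s | Slope per SD | Limit reached at | Controls expected beyond it |
|---|---|---|---|---|
| 0.60 | 0.37 | 0.090 | 4.6 SD | 0.002 |
| 0.65 | 0.57 | 0.138 | 3.0 SD | 1.6 |
| 0.70 | 0.79 | 0.191 | 2.1 SD | 17 |
| 0.75 | 1.06 | 0.256 | 1.6 SD | 58 |

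The slope is taken at the mean, so it is somewhat too steep and the counts are rough. They do show where the trouble starts: almost nobody at 0.60, one or two patients at 0.65, many at 0.70.

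**Step 3: simulation.** 300 trials per setting, n = 2115, 60 sites, 59% v 52%. Each trial was checked for a maximum of the identity-link likelihood with every fitted risk strictly inside 0-1. This was done without a site term and with a penalised site effect (SD 0.05) as an approximation to the random effect. The Monte Carlo error of a percentage is at most √(0.25/300) ≈ 3 points. The same s was used for every covariate type, so the c-statistic label is approximate for binary covariates.

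Admissible interior fit, without / with site effect:

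| c-statistic | Continuous (1 or 5) | 3 binary | 5 binary |
|---|---|---|---|
| 0.60 | 97-100% / 97-100% | 100% / 100% | 100% / 100% |
| 0.65 | 44-82% / 29-66% | 100% / 100% | 100% / 100% |
| 0.70 | 1-10% / 0-1% | 100% / 96% | 98% / 20% |
| 0.75 | 0-2% / 0% | 100% / 25% | 86% / 0% |
| 0.80 | 0-1% / 0% | 100% / 0% | 54% / 0% |

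With no covariates, as in the site-only analysis, the fit was admissible in 100% of trials either way.

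Two further simulations at the same size, fitted without a site term, agree for continuous covariates. One found failure (no convergence, or fitted risks outside 0-1) in 1% of trials at about 0.61, 58% at 0.66 and 100% at 0.75. The other found an admissible fit in 99% at 0.59, 59% at 0.65, 4% at 0.70 and 1% at 0.74. It also gave 99% with three binary covariates at 0.70 and 15% with five at 0.72. For five binary covariates the runs without a site term therefore disagree (98% at 0.70 and 86% at 0.75, against 15% at 0.72), and no firm figure should be quoted.

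**Step 4: the alternative.** In the Step 3 trials, a logistic model with marginal standardisation converged every time. It gave mean risk differences of −0.067 to −0.072 against a true value of about −0.07. At c-statistic 0.75-0.80 its empirical SE was 0.018-0.021, against 0.021-0.023 unadjusted. In a separate run of 300 trials the mean model-based SE was 0.0195 and the empirical SE 0.0193. These checks fitted no site effect and did no imputation.

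**The case against.** The best answer is that everything turns on covariates the protocol has not yet named. Weak covariates, or a few binary ones, fit without difficulty. The list, its coding and any fallback belong naturally in the statistical analysis plan, which is not shown. This stands in large part. It rules out saying that the model usually cannot be fitted once any prognostic covariate is added, and it rules out treating the absence of a stated fallback as a fault. It does not remove the point, because the link function and the policy of choosing strong predictors are both fixed in the protocol.

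Three further inferences are tempting and are not supported:

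- **That the trial's main result may be unobtainable.** The section names two effect measures without ranking them. The Poisson log-link model accepts any positive fitted mean, so it does not fail in this way, and the site-only risk difference fitted in every simulated trial.
- **That covariates would be picked after seeing the data.** The section fixes them a priori and excludes selection on imbalance, univariable significance or stepwise methods.
- **That invalid standard errors, or failure across imputed data sets, have been shown.** Coverage of the identity-link estimate was not simulated, and neither was imputation. A constrained maximum on the boundary still exists. The difficulty is getting usable inference from it.

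It is also fair to say that the simulated covariates act on the log-odds scale, which favours the logistic model. If risks were truly additive and stayed within limits, the identity link would do better than shown.

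**Conclusion.** The point holds conditionally. If the covariates are continuous with a joint c-statistic of about 0.70 or more, the model as written is likely to fail or reach a boundary: 0-1% admissible fits with the site effect, and at most 10% without it. At 0.65 the outcome is uncertain (29-66% with the site effect, 44-82% without). At 0.60 the fit is near-certain. Three binary covariates up to about 0.70 usually fit.

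These figures rest on assumed covariate strengths, log-odds covariate effects, a modest site effect and the planned size of 2115 analysed. The site-only risk difference, the relative risk model and the sample size of 2250 are unaffected. The change is worth making before outcomes are seen: the specified model is dependable only where adjustment brings little of the precision the protocol wants from it, and a replacement without this weakness costs little.

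**What to change.** In Protocol 5.2.2, for the covariate-adjusted primary analysis:

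- Specify a logistic model for 90-day mortality with a site effect and the a priori covariates.
- Obtain the risk difference by marginal standardisation: predict each patient's risk under each allocation, average, and subtract. The relative risk can come from the same predictions if wanted. State how the site effect enters the averaging.
- Use delta-method or bootstrap standard errors, pooled over the imputed data sets.
- Keep the identity-link model for the site-only analysis if desired.

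The target need not change. Under randomisation and with no interaction on the risk scale, the identity-link coefficient and the standardised difference both estimate the average risk difference on which the sample size is based.

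The cost is revised wording, a little more code, and an estimate obtained in two steps instead of read from one coefficient. No extra patients or data are needed. Because the checks above fitted no site effect, the analyst should try the full procedure, with site effect and imputation, on simulated data before it is finalised.

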### 5.2.3 Interim analysis

A single interim analysis of the primary outcome will be carried out after the recruitment and follow-up of 1125 patients using a Peto-Haybittle stopping rule ( $P < 0.001$ ) to recommend early termination due to either effectiveness or harm. Further interim analyses will be performed if requested by the DMEC.

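### The Poisson model named for relative risk has no stated variance correction; fitted as written, its standard errors would be about 1.5 times too large at the planned mortality

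*Protocol*

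**What the plan says.** Section 5.2.2 of the protocol estimates the effect on 90-day mortality in two ways, both by generalised linear mixed models with a random effect of site. The absolute risk reduction comes from the binomial family with identity link. The relative risk comes from "the Poisson family and log link to estimate relative risk".

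The same section carries these models further:

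- Secondary outcomes: "Analyses of secondary outcomes will use similar GLMMs with the binomial/Poisson family for binary outcomes".
- Subgroups: the treatment-by-subgroup interaction is tested "in the adjusted GLMM for the primary outcome on the relative risk scale". Severity of acidosis is named as one of the key subgroups.

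No section mentions a robust (sandwich) variance or any other correction for fitting a Poisson likelihood to a yes/no outcome. No section rules one out either, and 5.2.2 refers the description of all analyses to a statistical analysis plan, which was not available for this point.

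Section 5.1 sets the sample size on the absolute scale: "To achieve 90% power to detect a clinically meaningful absolute reduction in 90-day mortality of 7" percentage points, from 59% to 52%, with 6% allowed for withdrawal or refusal and 2,250 patients recruited.

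**The concern.** Ninety-day mortality is binary, with variance p(1-p). The Poisson likelihood takes the variance to be p. For a rare event the two are nearly equal. At a mortality above 50% they are not. The point estimate of the relative risk remains usable, but its model-based standard error is too large. The random site effect does not repair this: it can add variance to the model but cannot remove the excess that the Poisson family already assumes.

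If the model is fitted as named and its default standard errors are reported, relative-risk intervals will be too wide and P values too large. A real 7-point reduction could then be significant as a risk difference and not significant as a relative risk in the same report. The subgroup tests are more exposed, because the protocol gives them no risk-difference counterpart.

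**Working it through.** **Inputs.** Control 59%, intervention 52%, two-sided 5%, 90% power and 6% loss (section 5.1); 1:1 allocation (section 4.4.1). Section 5.1 does not state sidedness. Two-sided is assumed because the interim rule in section 5.2.3 is "to recommend early termination due to either effectiveness or harm", and because a one-sided test gives 1,835 recruited, which does not match.

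**Step 1: reproduce the plan's figure.** With pooled variance, mean risk 0.555 and no continuity correction:

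n per arm = [1.960 × sqrt(2 × 0.555 × 0.445) + 1.282 × sqrt(0.59 × 0.41 + 0.52 × 0.48)]² / 0.07² = 1,058 after rounding up.

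Total 2,116; divided by 0.94 this is 2,252, against 2,250 stated. Analysed per arm at 2,250: 2,250 × 0.94 / 2 = 1,057.5, where power for the absolute difference is 90.0%. The protocol's sample size is sound.

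**Step 2: the two standard errors of log RR at 1,057.5 per arm.**

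- Binomial (what a robust variance estimates): sqrt(0.41/(1,057.5 × 0.59) + 0.48/(1,057.5 × 0.52)) = 0.0391
- Poisson, model-based: sqrt(1/(1,057.5 × 0.59) + 1/(1,057.5 × 0.52)) = 0.0585
- Ratio: 0.0585 / 0.0391 = 1.50

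For a single risk p the factor is 1/sqrt(1-p): 1.44 at 52% and 1.56 at 59%.

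**Step 3: consequences for the planned effect.** RR = 0.52/0.59 = 0.881; log RR = -0.1263.

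| | Model-based Poisson | Robust |
|---|---|---|
| Expected 95% interval, exp(-0.1263 ± 1.96 × SE) | 0.786-0.988 | 0.816-0.952 |
| Power, Phi((0.1263 - 1.96 × SE)/0.0391) | 61.7% | 89.8% |

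Under no effect at 55.5% mortality the ratio is 1/sqrt(0.445) = 1.499. The real two-sided type I error is then 2 × (1 - Phi(1.96 × 1.499)) = 0.33%. At the planned effect, a nominal 95% interval covers about 99.7%.

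**Step 4: simulation.** With 20,000 simulated trials of 1,057 per arm and no site variation, the planned effect was detected in 62.1% with model-based errors, 90.5% with robust errors and 90.5% on the risk difference. With 60 sites and assumed site standard deviations of 0.2 and 0.4 on the logit scale (not given in the protocol; 150 trials each, sites fitted as fixed effects), detection was 58.7% and 55.3% with model-based errors, against 90.7% and 92.7% with robust errors.

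**Step 5: subgroups and other outcomes.** As an illustration, take an interaction that a correct test would detect with 80% power, so a shift of 1.960 + 0.842 = 2.802 standard errors. At the same ratio, the model-based test detects it with probability Phi(2.802 - 1.96 × 1.495) = Phi(-0.128), about 45%. For receipt of renal support, section 2 gives 50% in comparable patients, so the factor is 1/sqrt(0.5) = 1.41. For an outcome at 10%, an illustrative figure, it would be only 1/sqrt(0.9) = 1.05.

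**The case against.** The strongest objection is that this rests on silence. The protocol names a family and a link; it does not say that uncorrected standard errors will be used. The variance estimator is the kind of detail a protocol often leaves to the SAP, and the Poisson/log model is acceptable once a robust variance is added. This stands in part: the SAP may already settle the matter, and it cannot be said that the trial has chosen uncorrected errors. The point survives because the protocol itself fixes the likelihood, and that likelihood, fitted as written, gives wrong error bars for a common binary outcome.

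A reader might infer three stronger things, and the protocol supports none of them.

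- *That the trial is underpowered.* The 90% is claimed for the absolute reduction, which the binomial/identity model estimates with the right variance. That figure reproduces, and no power is promised on the relative-risk scale.
- *That false claims of benefit or harm become more likely.* The error runs the other way: type I error falls to about 0.3%.
- *That there are two rival primary tests.* Section 5.2.2 describes two estimates of effect, not two tests. Neither it nor section 5.2.3 says which scale supplies the P value, but that is commonly left to the SAP.

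The site simulation used fixed rather than random site effects, so it supports the closed-form result without exactly reproducing the planned model.

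**Conclusion.** The point holds in limited form. Section 5.2.2 specifies Poisson/log mixed models for the relative risk of binary outcomes, and for the subgroup interaction tests, without stating a robust variance. With model-based standard errors, inference on 90-day mortality would be conservative by a factor of about 1.5 in the standard error. Power on that scale would be about 62% instead of about 90%, and the interaction tests would be weakened in the same way. The effect shrinks for rarer outcomes.

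The risk-difference analysis and the sample size are unaffected. The figures assume the planned event rates, 6% loss, two-sided testing and no covariate adjustment. They apply only if no correction is specified elsewhere.

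**What to change.** In section 5.2.2, and in the SAP if it is not already there, state that every Poisson/log model of a binary outcome uses robust (sandwich) standard errors, including the models for subgroup interactions and binary secondary outcomes. Alternatively, obtain the relative risk by marginal standardisation from a logistic model, with delta-method or bootstrap standard errors.

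As a secondary clarification, state that the final P value and the interim P<0.001 rule are taken from the risk-difference scale on which the sample size was set.

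Both changes are wording only. The methods are in standard software and need no extra data, patients or time. They are best made before the interim analysis.
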